## 5.2 Exploratory Safety Analyses

TEAE summaries will be presented by yearly intervals for both treatment arms using the prevalence of new and ongoing events during each ibrutinib/placebo treatment duration interval (> 0-1 years, > 1-2 years, > 2-3 years, > 3-4 years, > 4-5 years, > 5-6 years, > 6-7 years) and for the overall TEAE period. Specifically, the treatment duration interval > 0-1 years includes all subjects who received ibrutinib/placebo treatment up to 1 year; > 1-2 years includes all subjects who received ibrutinib/placebo treatment more than 1 year and up to 2 years, etc.

For the determination of yearly prevalence, newly occurring TEAEs in the respective treatment duration yearly-interval as well as TEAEs still ongoing from the previous treatment duration yearly-interval will be included. Ongoing events for a subject from previous time period are only included in the next time period when the subject is at risk (i.e. within 30 days of last ibrutinib/placebo dose date) at the start of the next time period.

The prevalence of TEAEs will be summarized across yearly-intervals by MedDRA SOC and PT for all TEAEs, grade 3 and higher TEAEs, SAEs and TEAEs related to ibrutinib/placebo.

In addition, all TEAEs by SOC and PT will be summarized across yearly intervals for the following:

- subjects who discontinued ibrutinib for any reason other than PD vs. who did not discontinue ibrutinib
- subjects who discontinued ibrutinib for any reason other than PD after achieving BOR of SD or PR vs. CR

TEAEs leading to death will be summarized by SOC and PT at the study-duration yearly interval when the subject died. Study duration is considered instead of treatment duration in order to include events that started prior to 30 days after ibrutinib/placebo discontinuation, and for which death may have occurred outside of that time period.

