## 5 SAFETY ASSESSMENTS

Safety data will be summarized by treatment for the safety population unless otherwise indicated. [Table 7](#) summarizes the safety analyses to be carried out. AEs will be coded in accordance with the Medical Dictionary for Regulatory Activities (MedDRA). Severity of AEs will be graded by the investigator according to the NCI Common Terminology Criteria for Adverse Events (NCI-CTCAE) v4.03.

The treatment-emergent period is defined as the period from the date of the first dose of study treatment up to 30 days after the date of the last dose of study treatment or the day before initiation of subsequent anti-cancer therapy, whichever comes first.

The treatment-emergent adverse events (TEAEs) are those events that occur or worsen during the treatment-emergent period or that are related to the study treatment. TEAEs or deaths related to COVID-19 infection will be summarized or listed separately. All laboratory values will be converted to and reported as international standard (SI) units. In general, only data from the central laboratory will be summarized and analyzed. When central lab values are missing and local lab values are available, local lab values will be used. Laboratory parameters will be graded using the NCI CTCAE v4.03. Unless otherwise specified, only baseline and post-baseline values collected during the treatment-emergent period will be included in the safety analysis.

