### 5.1 Exposure-Adjusted Incidence Rate

Exposure-adjusted incidence rate (EAIR) takes into account the patients' exposure time in quantifying the risk of an AE. For a given AE, EAIR is defined as the rate of the number of patients who experience at least one event over total time at risk for all subjects (Zhou, et. al.

2015; Jia, et. al. 2020). EAIR "adjusts for exposure" by accounting for the variability in patients time at risk as opposed to crude incidence rates, which divides the number of patients with events by the total number of patients. The time at risk is different for patients who have experienced the event and subjects who are event-free throughout the treatment-emergent period.

For patients with at least one event, the time at risk is the time from first dose date to the start date of the first event. The choice to restrict the time at risk to the onset of first event is due to EAIR's epidemiological origin and is based on the assumption that occurrences of multiple events are interdependent. Hence, for patients with events, the time at risk can be represented, in patient-years at risk, as:

$$(Start\ date\ of\ the\ first\ event - first\ dose\ date + 1)/365.25 \quad (equation\ 1)$$

For patients with no event, the time at risk is the time from the first dose date to the end of the treatment-emergent period which can be represented, in patient-years at risk, as:

$$(Last\ dose\ date + 30\ days - first\ dose\ date + 1)/365.25 \quad (equation\ 2)$$

The *total patient-years at risk* is the sum of the patient-years at risk for all subjects. For patients with events, patient-years at risk is calculated using equation 1, while for patients with no event, patient-years at risk is calculated using equation 2.

The *100 patient-years at risk* is the total patient-years at risk divided per 100 patients and can be interpreted as the average of length time (in years) to observe the first onset of AE if 100 patients were treated for 1 year.

For a given AE, the EAIR is represented as the number of patients with events per 100 patient-years at risk:

$$(Number\ of\ subjects\ with\ events/total\ patient-years\ at\ risk)*100,$$

or, equivalently

$$Number\ of\ subjects\ with\ events/100\ patient-years\ at\ risk$$

An equivalent interpretation of EAIR can be expressed as the "average number of patients experiencing the event of interest if 100 patients were treated for 1 year".

EAIRs may be summarized for all TEAEs, fatal TEAEs, and serious TEAEs.

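### SAP 5.1 and 5.2: equation 2 runs past the SAP's own end of time at risk, and the yearly TEAE prevalence has conflicting membership rules and no stated denominator

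*SAP*

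**What the plan says.** **Exposure-adjusted incidence rate (EAIR).** SAP Section 5 ends the treatment-emergent period 30 days after the last dose of study treatment or "the day before initiation of subsequent anti-cancer therapy, whichever comes first". SAP 5.1 builds on this: "For patients with no event, the time at risk is the time from the first dose date to the end of the treatment-emergent period". Equation 2, given as the representation of that time, is (last dose date + 30 days − first dose date + 1)/365.25, with no term for subsequent therapy. Subjects with an event use equation 1, which stops at the first event. SAP 5.1 makes EAIR output optional.

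**Yearly prevalence.** SAP 5.2 describes the intervals by how long subjects were treated: "the treatment duration interval > 0-1 years includes all subjects who received ibrutinib/placebo treatment up to 1 year", and the next one "includes all subjects who received ibrutinib/placebo treatment more than 1 year and up to 2 years". Its following paragraph sets the numerator: "newly occurring TEAEs in the respective treatment duration yearly-interval as well as TEAEs still ongoing from the previous treatment duration yearly-interval will be included". It then limits the carry-over: "Ongoing events for a subject from previous time period are only included in the next time period when the subject is at risk", explained as "within 30 days of last ibrutinib/placebo dose date" at the start of that period. Section 5.2 does not say what the counts are divided by.

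**The concern.** Section 5.1 gives two rules for the same quantity, and they differ whenever an event-free subject starts new therapy within 30 days of the last dose. The numerator follows Section 5, so an unrelated event that starts after new therapy is not a TEAE. If the denominator follows equation 2, the time after new therapy still counts as time at risk, and the EAIR comes out too low. The design assumes a PFS hazard ratio of 0.60, so the timing of progression and switching may differ between arms, and the error need not cancel.

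In Section 5.2 the membership sentence and the carry-over rule cannot both define the same intervals. Under the first, taken literally, a subject treated for three years belongs to one interval only. Under the second, the same subject can contribute to several. A programmer has to choose, and the denominators differ greatly. The SAP revision history says these analyses were added to assess cumulative safety, and a by-year profile needs a defined risk set to do that.

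**Working it through.** The plan gives no figure that depends on these definitions, so there is nothing to reproduce. The check compares the definitions and then sizes the gap on assumed inputs.

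**1. EAIR, one subject (assumed dates).** First dose day 1, last dose day 365, new therapy day 375.
- Equation 2: 365 + 30 − 1 + 1 = 395 days.
- Section 5 definition: the period ends on the earlier of day 395 and day 374, so 374 − 1 + 1 = 374 days.
- Excess: 21 days. The largest possible excess is 30 days, or 30/365.25 = 0.082 patient-years, when new therapy starts the day after the last dose.

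**2. EAIR, event-free subjects as a group.** Assumed inputs: mean exposure m of 0.5 to 3 years; a share f of 10% to 50% starting new therapy within 30 days; g = 1 or 15 post-dose days remaining in the period for those subjects.

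Overstatement = (m + 30/365.25) / (m + 30/365.25 − f(30 − g)/365.25) − 1

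- m = 2, f = 0.1, g = 15: 2.0821/2.0780 − 1 = 0.2%.
- m = 2, f = 0.5, g = 1: 2.0821/2.0424 − 1 = 1.9%.
- Over the whole assumed range: 0.1% (m = 3, f = 0.1, g = 15) to 7.3% (m = 0.5, f = 0.5, g = 1).

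This is the error in event-free time. The EAIR denominator also holds time from subjects with events, which is unaffected, so the relative error in the EAIR is smaller.

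**3. Prevalence, the two rules side by side.** Take a subject whose last dose is on day 350. At the start of year 2 (day 365.25) the 30-day tail still has 350 + 30 − 365.25 = 14.75 days to run. The carry-over rule counts an ongoing event in year 2, but the membership sentence leaves the subject out of the > 1-2 years interval.

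**4. Prevalence, size of the choice.** Assumed: N = 330 (three quarters of the planned 440, from the 3:1 allocation) and exponential time on ibrutinib/placebo, so that S(k) = 2^(−k/median). For year 2, the literal denominator is N[S(1) − S(2)] and the at-risk denominator is N·S(1).

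| Assumed median duration | Literal | At risk | Ratio |
|---|---|---|---|
| 1 year | 82 | 165 | 50% |
| 2 years | 68 | 233 | 29% |
| 3 years | 54 | 262 | 21% |
| 5 years | 37 | 287 | 13% |

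Under this model the ratio, 1 − 2^(−1/median), is the same in every interval. The at-risk column leaves out the 30-day tail. Adding it for a 3-year median gives 330 × 2^(−0.918/3) = 267 instead of 262.

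**5. Prevalence, mixing the rules.** In a simulation with median duration 3 years, AE onset rate 0.3 per year and mean AE duration 0.5 years (all assumed), year-2 prevalence was 28.3% with the at-risk set in numerator and denominator, and 21.9% with the literal group in both. At-risk events divided by the literal group gave 137% (28.3%/20.6%), which is impossible as a prevalence.

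**The case against.** **On prevalence.** A reader might infer that Section 5.2 settles on counting only subjects whose total treatment ended in the given year, so that year 1 rests on early stoppers and every interval is distorted. The documents do not support that. The sentence says neither only nor total, and no denominator is given. The carry-over rule lets one subject enter several intervals. The section's last paragraph places fatal TEAEs by study year and contrasts study duration with treatment duration, which treats both as time axes. Where the SAP does group subjects by total duration, in Section 4.1, it says so plainly. All this points to an at-risk intention. It does not remove the problem: the carry-over rule governs ongoing events only, and the one sentence on membership says something different.

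**On the EAIR.** It is tempting to add that equation 2 also counts time outside the treatment-emergent period after death or data cutoff. Section 5 ends the period at neither, so this is a gap and not a contradiction. The SAP also does not say what the last dose date is for a subject still on treatment at cutoff. Protocol 11.4.2 requires a death within 30 days of last dose to be reported as a serious event, so such a subject would normally have an event in the any-TEAE or serious-TEAE rates and use equation 1. The words of Section 5.1 do state the right end point; the formula departs from them.

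**On importance.** Section 5.2 is exploratory, EAIRs are optional, the protocol plans no formal safety testing, and the main TEAE summaries in SAP Table 7 do not need either definition. This stands, and it limits the weight of the point.

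**Conclusion.** Two minor inconsistencies hold.

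- **SAP 5.1:** equation 2 contradicts the definition it is meant to represent. The error is confined to event-free subjects who start new therapy within 30 days of last dose, is at most 30 days each, and lowers the EAIR. Event-free time is overstated by about 0.2% to 1.9% at an assumed mean exposure of 2 years.
- **SAP 5.2:** interval membership, read literally, conflicts with the carry-over rule, and the denominator is undefined. The finding is an unresolved specification, not a wrong denominator definitely prescribed. The choice matters: in year 2 the literal group is 13% to 50% of the at-risk set for assumed median durations of 5 years down to 1 year.

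The sizes are illustrations: exposure, switching, AE rates and the exponential shape are assumed, not taken from the documents. Whether the arms would be affected unequally cannot be judged from the plan. Efficacy analyses, interim rules and type I error are untouched.

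**What to change.** **SAP 5.1.** Replace equation 2 with (the earlier of last dose date + 30 days and the day before subsequent anti-cancer therapy − first dose date + 1)/365.25. Capping also at death and data cutoff is a sensible addition. If adopted, state it as a new rule and say which date serves as last dose for subjects still on treatment at cutoff.

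**SAP 5.2.** Replace the membership sentence with an explicit denominator: for each yearly interval, all safety-population subjects who are on ibrutinib/placebo, or within 30 days of their last dose of it, at the start of that interval, whatever their later treatment duration. Draw the numerator from the same subjects, so that prevalence cannot exceed 100%.

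**Cost.** A few sentences and small programming changes. No new data should be needed, since the date of subsequent therapy is already required for PFS censoring and for the treatment-emergent period, and the date of death for OS.

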## 6 APPENDICES

### 6.1 Algorithm for Defining $\geq 2$ Consecutive Missing Assessments

This algorithm is used for the PFS primary analysis for US regulatory submission and for the PFS sensitivity analyses for Other Regions.

This study has 2 planned imaging schedules: every 4 cycles (1 cycle = 28 days) from Cycle 5 through Cycle 37, and every 6 cycles afterwards (see [Table 8](#) below). Based on the change between the schedules, one transition of the imaging schedule (time period 2 in [Table 8](#) below) is described as follows:

- When the adequate non-PD assessment occurs at Cycle 33, the next two subsequent assessments are planned at Cycle 37 (+4 cycles) and Cycle 43 (+6 cycles), respectively.

This algorithm will follow two steps in sequence:

1. Step 1 (Columns 2-4 in [Table 8](#)): Calculate the study day of the adequate non-PD assessment. Map the adequate non-PD assessment to a closest scheduled visit based on the study day using the midpoint time period window (see footnote of [Table 8](#) for details). Once the assessment is mapped to a scheduled visit, the imaging interval for the next two subsequent consecutive visits can be decided based on the planned imaging schedule.
2. Step 2 (column 5 in [Table 8](#)): Calculate the maximum gap in days allowed for the next two subsequent visits based on the planned imaging interval plus the specified window (+/- 28 days) for each visit.

If the gap between the adequate non-PD assessment and the next adequate assessment or death exceeds the maximum gap, the subject has a  $\geq 2$  consecutive missing assessments and its PFS will be censored at the last adequate non-PD assessment before the missing interval. If there are 2 more missing intervals, the PFS will be censored at the last adequate assessment before the first missing interval. If the first missing interval occurs right after the randomization date, then PFS will be censored at the randomization date.

**Table 8. Algorithm for defining  $\geq 2$  consecutive missing assessments**

Time Period	Adequate Non-PD Assessment		Imaging Schedule for the Two Subsequent Consecutive Assessments after the Adequate Non-PD Date	Maximum gap & in Days Allowed between the Adequate Non-PD Date and Next Adequate Assessment or Death
	Scheduled Visit	Study Day Time Period Window #		
1	Cycle 5 to Cycle 29	Day 2 - Day 841	every 4 cycles (112 days)	$280 = (112+28)*2$
2	Cycle 33	Day 842 - Day 953	4 cycles (112 days) & 6 cycles (168 days)	$336 = (112+28) + (168+28)$
3	Cycle 37 and up	Day 954 and up	every 6 cycles (168 days)	$392 = (168+28)*2$

#: The visit window for each visit is based on the midpoint between two scheduled visits (i.e. target day +/- the half planned interval between two scheduled visits). The study day in time period 1 can be as early as one day after randomization (Day 2). If the adequate non PD assessment is the same as or earlier than the midpoint, it will be assigned to the earlier visit, and if the assessment is later than the midpoint, it will be assigned to the later visit. Study day is calculated in reference to the randomization date. 1 cycle = 28 days.

&: A 28 day window is allowed to provide more flexibility regarding the timing of the data collection for disease assessment considering the COVID 19 situation and the indolence of first line follicular lymphoma

## 8 REVISION HISTORY

**Table 9. SAP Version History Summary**

Version Number	Date	Descriptions
1.0	08Dec2020	Original version
2.0	19Oct2021	Amendment summary: Below are the major changes made. 
 
1. Update secondary endpoints and sample size determination per protocol amendment 2 dated March 10, 2021.
 
2. Modified the second interim analysis boundaries from Rho spending function to Lan-DeMets alpha spending function with O'Brien-Fleming parameter.
 
3. Update the alpha spending and testing procedure for secondary endpoints per protocol amendment 2.
 
4. Remove interim analysis for ORR.
 
5. Clarify the description regarding stratification factors in Part 1.
 
6. Add infusion related reaction rate to the sequential testing procedure and rank order for the secondary endpoints.
 
7. Clarify sections on interim and final analyses.
 
8. Add estimands and summary of estimand attributes for the primary and key secondary endpoints per ICH E9(R1).
 
9. Add the subgroup definition table for subgroup analysis.
 
10. Add descriptive summary of COVID-19 impact in disposition, safety, compliance; also add sensitivity and/or supplementary analysis for efficacy endpoints.
 
11. Add the description to handle COVID-19 deaths in the PFS primary and supplementary/sensitivity analyses.
 
12. Update the analyses for secondary endpoints.
 
13. Add analyses for PFS by IRC, ORR by IRC and DOR by IRC.
 
14. Add detailed analyses for exploratory endpoints such as CR30 and patient reported outcomes (PROs).
 
15. Add detailed definition of treatment emergent adverse events, and summary for treatment emergent adverse events and deaths related to COVID-19 infection.
 

3.0	29Apr2022	Amendment summary: 
 
1. Add time to worsening for FACT-Lym scores.
 
2. Update censoring rule due to subsequent anti-cancer therapy for PFS
 
3. Revise sample size to be 445 as one subject was randomized twice
 
4. Add OS futility analysis at IA2 and modify boundaries for PFS analysis
 
5. Update extent of exposure variables.
 
6. Signatory for programming team changed
 
7. Added a figure of the testing procedure
 

		8. For the stratified efficacy analyses, stratification factors with small strata (<10 events) were removed. A pre-specified selection method and reference were given in the main text.
4.0	13Feb2023	Amendment summary: 
 
1. Removed Part 2 language.
 
2. Update PFS primary censoring rule to include censoring for COVID-19 deaths without PD.
 
3. Added OS interim analysis at PFS primary analysis and modify OS final analysis timing. Added OS boundary values and table.
 
4. Clarified ECOG and FLIPI-1 source data for subgroup analysis.
 
5. Removed “Section 6 Changes in Protocol Planned Analysis” as changes in SAP v3 have been reconciled with Protocol Amendment 4.
 
6. Added algorithm for defining 2 or more missed assessments.
 

5.0	01Jun2023	Amendment summary: 
 
1. Update PFS primary censoring rule to include censoring for subjects who missed two or more consecutive overall disease assessments prior to the PFS event.
 
2. Change the superiority boundary for the interim OS analysis from Lan-DeMets alpha spending function with O’Brien-Fleming boundary to Haybittle-Peto boundary.
 

6.0	01Mar2024	Amendment summary: 
 
1. Update the futility analysis of PFS (IA1) and the futility analysis of OS at PFS IA2 by spending 0.00001 alpha to ensure strict control of family wise error rate.
 
2. Update the PFS primary censoring rules to not censor for COVID-19 deaths without PD. Accrue additional PFS events to make up for the potential impact of COVID in accordance with FDA’s COVID-19 guidance.
 
3. Update the PFS primary censoring rule, for US regulatory submission only, to include censoring for subjects who missed two or more consecutive overall disease assessments, regardless of whether or not a PFS event subsequently occurs.
 
4. Update the algorithm to defining <math>\geq 2</math> consecutive missing assessments to include subjects who missed two or more consecutive overall disease assessments, regardless of whether or not a PFS event subsequently occurs, and specifying a 28-day visit window.
 
5. Added “Section 5.1 Exposure-Adjusted Incidence Rate”
 
6. Added “Section 8.1 Changes to Planned Analyses in the Protocol”
 

v6.0 Addendum	17Apr2024	Exploratory efficacy and safety analyses were added to further assess the efficacy and cumulative safety of ibrutinib as administered in the protocol,
7.0	13May2024	Amendment summary: 
 
1. Incorporate SAP v6 addendum
 

 <small>An AbbVie Company</small>	PCYC-1141-CA Analysis Study Statistical Analysis Plan	Page 33 of 33
		
 
 
 
a. Updated Section 1.2.3 by adding TTP and DOCR as exploratory endpoints
 
b. Updated Table 4.1 by adding the definition and analyses method of TTP and DOCR
 
c. Added "Section 4.1 Exploratory Efficacy Analyses"
 
d. Added "Section 5.1 Exploratory Safety Analyses"
 
 
 
2. Remove the 0.00001 alpha allocation at the futility analysis of PFS (IA1) and the futility analysis of OS at PFS IA2. 
 
a. Update Table 3.1, Table 3.2, Table 4.1, Table 4.2, and Figure 2.
 
 
 

## 8.1 Changes to Planned Analyses in the Protocol

1. IRC will be implemented to do the overall disease assessment based on Cheson 2014 (Lugano Classification Criteria). A sensitivity/supplementary analyses will be conducted for the endpoints PFS, ORR and DoR using the IRC assessment.
2. The superiority boundary for the interim OS analysis was changed from O'Brien Fleming boundary to Haybittle-Peto boundary.
3. Per US FDA information request, PFS primary censoring rules was updated to include censoring of subjects with  $\geq 2$  consecutive missed assessments at the last adequate assessment before the missing interval, regardless of whether or not a PFS event subsequently occurs.
